### **2.3. Vulnerable subjects**

The study will not enroll high-risk drug and alcohol users because a preponderance of evidence indicates that brief intervention alone is not sufficient to address severe (high-risk, dependent) substance use. While primary care-based pharmacotherapy can be effective for drug and alcohol dependence, these more intensive interventions are out of the scope of the proposed study. Pregnant women are excluded because the potential risks to the fetus of ongoing drug use changes the threshold for intervention, may alter the motivation of the patient to change their use, and can hinder follow-up at 6 months. We will offer treatment referrals to high-risk and pregnant patients, as detailed in section 4.3. No other vulnerable populations are enrolled.

[figure not shown]
## **3. Methods and procedures**

### **3.1. Study conditions, methods, and procedures**

#### **3.1.a. Phase 1: Development of CDS:**

We will develop the CDS using accepted best practices, and conduct usability testing of the SUSIT CDS tool following a standard and widely adopted approach. This is a 3-phase process consisting of definition, usability testing, and clinical testing, as portrayed in Figure 2.

Figure 2: Procedure for developing CDS

*Definition* of the CDS tool consists of specifying the basic content of the brief intervention and soliciting the opinions of practicing PCPs and an expert panel on clinical information requirements and design preferences. The expert panel will include nationally recognized HIT experts as well as a medical director and two primary care providers from the participating study sites. Structure of the CDS is based on the Brief Negotiated Interview (BNI), which assists providers in conducting a brief (3-5 minute) intervention by guiding them through the four major components of a brief negotiated interview: raising the subject, providing feedback, enhancing motivation, and negotiating a plan.

As an initial step in content development, semi-structured interviews will be conducted with a purposively selected sample of 5 PCPs from the Bellevue site. Interviews will elucidate the design elements most likely to impact 'perceived usefulness' and 'perceived ease of use' of the CDS component. Recommendations of PCPs and the expert panel will be reviewed by the investigators, and then incorporated by the software development team into a CDS prototype. The prototype design will follow accepted best practices for CDS, as defined by a growing body of heuristics developed for displaying guideline information for different types of systems and disease areas (that have emerged from systematic reviews and usability engineering).

*Usability testing:* The prototype CDS will be tested by PCP end-users recruited from Gouverneur Health, and Bellevue Hospital Center. Users will be given simulated clinical scenarios and asked to 'think-aloud' while interacting with the CDS. The user's interaction with the CDS will be recorded in its entirety by video screen recording software (capturing their computer screen, with no image of the participant), and digital audio recording. This data will be analyzed to identify usability issues and areas for potential optimization. We plan 3 cycles of usability testing.

[figure not shown]
*Clinical testing:* A refined prototype will then be tested in clinical practice by 5 PCPs. PCPs will be asked to use the CDS in their regular practice for 2 weeks, at the end of which they will participate in a semi-structured interview with the PI and will complete a structured questionnaire (modified TAM2) that gathers information on their attitudes and experiences with using the tool. Up to 45 patients will be recruited and enrolled following the procedures detailed in Section 5, and PCPs will be provided with screening results for those with moderate-risk drug use.

### 3.1.b. Phase 2: Screening Only (SO) vs. SUSIT

Phase 2 is conducted at Bellevue Hospital's Adult Primary Care Clinic and Virology Clinic. Adult patients of the participating PCPs will be recruited and enrolled following the procedures detailed in Section 5. The participating PCPs will receive screening results, CDS, and clinical reminders during the SUSIT condition, to help them address unhealthy drug use in their patients. The intervention that patients receive is determined by the period in which they are enrolled (i.e. Screening Only (SO)

vs. SUSIT), as indicated in Figure 3. Participating patients in both the SO and the SUSIT condition will enter responses to the tablet computer self-administered substance use screening tool. Screening is self-administered using a touch-screen tablet, and completed by patients in the waiting area prior to the clinical encounter. Substance use screening is part of a brief 'healthy lifestyle survey,' which also includes items on diet and exercise adapted from an existing health risk assessment. After the baseline medical encounter, patients will provide verbal responses to structured interviews. They will also complete a demographics form, and a self-administered computerized exit survey to ascertain whether their PCP provided elements of a substance use brief intervention during the medical visit, and various assessments described below. The exit survey will be administered again at any follow-up medical visits with the PCP that occur during the study period.

Figure 3. Study conditions

**Screening Only (SO) condition:** Patient and PCP are not presented with screening results. The PCP does not receive clinical decision support, or clinical reminders.

**SUSIT condition:** Following completion of substance use screening, the tablet computer presents screening results (including level of risk) to the patient for each substance used, asks them to identify their drug of most concern (DOMC), and assesses readiness and confidence to change behavior. Results are delivered to the PCP at the point of care, paired with clinical decision support tailored to the patient's screening results. This information is delivered on the tablet computer, which is handed to the PCP by a Medical Assistant. CDS guides the PCP through a brief intervention specific to the DOMC, recommends clinical actions pertaining to the substance and risk level, and generates a printed summary for the patient. At each scheduled follow-up medical visit, the PCP receives a clinical reminder containing a summary of the patient's substance use and level of risk, paired with CDS that guides them through a follow-up brief intervention. A member of the study team will call, email, or text patients prior to these scheduled follow-up medical visits, to confirm that they will be attending.

**Phase 2 SUSIT Condition at Enrollment Only Sites:** Enrollment only sites will participate only in the Phase 2 SUSIT condition. All research activity at these sites is conducted by NYU Research Staff. The NYU research staff will obtain consent and enroll study participants (including both PCPs and patients), and only those individuals who give consent for participation will have any involvement with the study at these sites. After obtaining consent, the NYU research staff will conduct assessments

with enrolled patients at the baseline, 3 month, and 6 month study visits.

Patient participant assessments in SO and SUSIT conditions (Table 1)

In both the SO and SUSIT conditions, study visits are at baseline (same day as the primary care visit), 3 months, and 6 months. Exit surveys ascertain what elements of brief intervention were conducted by the PCP, and are conducted at the baseline visit, the 3 month, the 6 month and at each follow-up medical visit. If the patient has not seen their provider in the last 3 months, they will not have to complete the survey. To minimize any potential for the RA to influence reporting, patients will self-administer the exit survey, prior to collection of additional substance use measures. PCPs will receive a clinical reminder for patients in the SUSIT condition, and may consequently address substance use differently than in the SO condition. For this reason, we will record scheduled follow-up medical appointments, and call, email or text participants several days prior to appointments.

At the baseline study visit, and at the 3- and 6-month study visits, the RA will administer substance use assessments: Timeline follow-back (TLFB), Composite International Diagnostic Interview, Second Edition, Substance Abuse Module (CIDI-SAM), for Spanish speaking patients the M.I.N.I (Mini-International Neuropsychiatric Interview) will be used as the measure of substance use disorder, because the CIDI is not currently available in Spanish, the Short Inventory of Problems for alcohol and drugs (SIP and SIP-DU), the first 8 items of the Patient Health Questionnaire (PHQ-8), and the Generalized Anxiety Disorder 7-item scale (GAD-7). Participants will provide hair samples for drug toxicology testing at the month-6 study visit. This will detect common drugs of abuse, as a means of corroborating self-report of recent drug use. If after repeated outreach attempts, and the participant is still not able to meet with RA in person, a phone interview will be scheduled with the participant for either the 3 or 6 month follow-up interview. This will be a one-to-one phone interview, with the RA or RC (whomever is conducting the interview) will be a private area. When scheduling the phone interview will ask the participant to ensure being in private space during the phone interview. For those participants that will have their 6 month interview by phone, the hair sample will become not applicable for those participants.

Chart review: Research staff will perform a structured chart review of the participant's medical record that examines the content of notes written by the participant's primary care provider(s) during the 12 months following study enrollment (inclusive of the date of enrollment). The chart review collects similar information to the patient exit survey; namely, documentation of any discussion by the primary care provider about drug, tobacco, or alcohol use. The chart abstraction form will be approved by the IRB.

Individual in-depth interviews with patient participants will characterize the acceptability to patients of conducting substance use screening and interventions in primary care. A purposive sampling approach will be used to select 12 patients who are already enrolled in the SO or SUSIT arm of the study. Those selected will represent a range of sex and age groups. The attitudes of patients are particularly important when addressing a stigmatized behavior such as substance use. While self-administered screening tools may allow for more honest reporting of stigmatizing behaviors, some patients might prefer face-to-face communication with their providers.

Table 1. Phase 2 Outcomes and measures

Outcome	Measures	Source	Collected at
Primary Outcome:			

Patient receipt of a substance use intervention	Audio recordings of medical visits, transcribed and coded with BAS scale	Audio recording of medical visit	Baseline and all follow-up PCP visits (SUSIT condition only)
	Patient exit survey: -Frequency of intervention -Elements of intervention	Patient (self-administered)	Baseline and all follow-up PCP visits
	Chart review -Frequency of intervention -Elements of intervention	Medical Record	Baseline and all follow-up PCP visits
Secondary Outcomes:			
Disclosure of substance use on screening	ACASIASSIST vs. TLFB and hair test results	Patient	Baseline 3- and 6-month study visit*
Self-reported drug and alcohol use	90-day TLFB	Patient	Baseline 3- and 6-month study visits
Drug or alcohol use severity	CIDI-SAM	Patient	Baseline 3- and 6-month study visits
Problems related to drug or alcohol use	SIP, SIP-D	Patient	Baseline 3- and 6-month study visits
Psychological well-being	GAD-7, PHQ-8	Patient	Baseline 3- and 6-month study visits
Biologic measure of any drug use	Hair testing	Lab result	6-month study visit*
Acceptability to patients of screening and interventions	In-depth interviews	Patient	Individual interviews with 6 patients in each study period

\* Hair testing will become not applicable for any patient participant that completes 6 month interview over the phone

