#### Quantitative data analysis (Phase 2):

The data structure follows a hierarchy of patient-level data nested within providers, during the SO vs. SUSIT study period. For analysis of the primary outcome, which is measured at the patient level, we will first examine whether any brief intervention occurred, in at least one visit, during the study period. For additional descriptive information we will count the number of visits in which an intervention occurred, and the number of elements of the brief negotiated interview documented in each visit. The “receipt of brief intervention” outcome analyses will use a generalized linear mixed model (i.e., multilevel logistic regression) with a random intercept and patients nested within primary care providers. The key explanatory variable will be treatment condition (SUSIT vs. SO). When the fixed effect of treatment condition is exponentiated, this coefficient indicates how the odds of receiving brief intervention are multiplied when an individual receives the SUSIT condition rather than screening only. Patient-level and PCP-level covariates (e.g., substances used, provider SAAS score) can be added to the multilevel logistic regression analysis if they are significantly related to the odds of intervention. Any patient-level covariates will be grand mean centered following our focus on treatment condition effects.

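### Tablet feedback given only in SUSIT may be credited to the PCP on the exit survey, and the plan has no check on this for the primary outcome

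*Combined protocol and SAP*

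**What the plan says.** Section 3.1.a builds the brief intervention from four components: "raising the subject, providing feedback, enhancing motivation, and negotiating a plan".

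Section 3.1.b describes what patients experience in each condition. Both groups complete the tablet screening in the waiting area. In SUSIT, "the tablet computer presents screening results (including level of risk) to the patient for each substance used"; the tablet then asks for the drug of most concern and "assesses readiness and confidence to change behavior". In SO, "Patient and PCP are not presented with screening results".

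After the encounter, patients in both conditions complete "a self-administered computerized exit survey to ascertain whether their PCP provided elements of a substance use brief intervention during the medical visit". The one reporting safeguard given is: "To minimize any potential for the RA to influence reporting, patients will self-administer the exit survey", ahead of the other substance use measures.

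Table 1 lists three sources for the primary outcome: audio recordings coded with the BAS (SUSIT only), the exit survey, and chart review. The last two carry no restriction by condition. For the analysis, section 3.2.a states that "we will first examine whether any brief intervention occurred, in at least one visit, during the study period", using a multilevel logistic model of SUSIT versus SO. It does not name the source that defines the event.

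**The concern.** The exit survey asks the patient to attribute content to a person. In SUSIT, similar content has just reached the patient from a device. The tablet's risk results clearly overlap with the feedback component, and its readiness and confidence questions touch on motivation. SO patients get neither. If some SUSIT patients credit the PCP with tablet content, the survey's false-positive rate is higher in SUSIT than in SO. That is differential misclassification in the direction of the study hypothesis.

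The at-least-one-visit rule adds to the exposure, because a single misattributed baseline report makes the patient positive for the whole study period. The self-administration safeguard is aimed at the research assistant's influence, not at confusion between tablet and PCP. The central hypothesis concerns higher rates of intervention by PCPs, so a survey odds ratio that partly reflects the tablet would not answer it.

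**Working it through.** **Is there a plan figure to reproduce?** No. The documents give 75 patients per condition. For the primary outcome they give no expected rates, effect size, alpha or power, and no error rates for the exit survey. What follows is illustrative.

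**Step 1. Compare the conditions before and after the visit.**

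| | SO | SUSIT |
|---|---|---|
| Tablet screening questions | Yes | Yes |
| Tablet shows risk results to patient | No | Yes |
| Tablet asks drug of most concern, readiness, confidence | Not described | Yes |
| Patient-facing tablet feedback at follow-up visits | Not described | Not described |
| Exit survey on what the PCP did | Yes | Yes |
| Audio coded with BAS | No | Yes |
| Chart review | Yes, with consent | Yes, with consent; no record access at the enrollment only sites |

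The difference that matters is tablet feedback at baseline.

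**Step 2. False odds ratio when PCPs behave identically.** Assumed inputs: true rate t equal in both conditions; survey sensitivity 0.85 in both; SO specificity 0.95; SUSIT specificity 0.90, 0.85 or 0.80.

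Observed rate = t × sensitivity + (1 − t) × (1 − specificity).

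For t = 0.30, SO: 0.30 × 0.85 + 0.70 × 0.05 = 0.290. SUSIT at specificity 0.85: 0.255 + 0.70 × 0.15 = 0.360. Odds ratio = (0.360/0.640) / (0.290/0.710) = 1.38.

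The last column is the chance of a significant result from a two-sided pooled two-proportion test with 75 per condition, an assumed alpha of 0.05, and clustering by PCP ignored.

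| True rate | SUSIT specificity | SO observed | SUSIT observed | False OR | Chance of p < 0.05 |
|---|---|---|---|---|---|
| 0.30 | 0.90 | 0.290 | 0.325 | 1.18 | 7.5% |
| 0.30 | 0.85 | 0.290 | 0.360 | 1.38 | 14.9% |
| 0.30 | 0.80 | 0.290 | 0.395 | 1.60 | 27.2% |
| 0.20 | 0.90 | 0.210 | 0.250 | 1.25 | 8.9% |
| 0.20 | 0.85 | 0.210 | 0.290 | 1.54 | 20.4% |
| 0.20 | 0.80 | 0.210 | 0.330 | 1.85 | 37.9% |

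**Step 3. A second parametrisation.** Suppose the survey is otherwise perfect, and a share m of SUSIT patients with no PCP intervention credit the tablet's content to the PCP. The SUSIT observed rate is then p + m(1 − p), where p is the true rate in both conditions. Same test.

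| True rate p | m = 5% | m = 10% | m = 20% |
|---|---|---|---|
| 10% | OR 1.53, 13% | OR 2.11, 35% | OR 3.50, 81% |
| 30% | OR 1.18, 7% | OR 1.37, 15% | OR 1.83, 43% |
| 50% | OR 1.11, 6% | OR 1.22, 9% | OR 1.50, 23% |

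If m is the same in both conditions, rejection stays at 5% when there is no true effect. The problem is therefore the difference between conditions, not misattribution as such. The bias is worst where the true rate is low.

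**Step 4. Can the other listed sources settle it?**
- Audio shows what the PCP said, but has no SO counterpart.
- Chart review draws on PCP notes, so patient misattribution cannot enter it. However, section 5.2 makes it depend on consent obtained from January 2019 onward, and patients who cannot be reached are not reviewed. Section 4.3.c says staff will not use the EHR to view patient information at the enrollment only sites, which take part only in SUSIT. Coverage may therefore differ by condition.

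Each source is a useful check, and neither is a complete replacement.

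**The case against.** The strongest reply is that the survey is described as asking about the PCP and the medical visit, whereas the tablet step happens beforehand in the waiting area. The items are not reproduced and may already separate the two. This stands: the text supports a risk of inflation, not a finding of it.

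Several further objections also stand:
- SO patients answer the same screening questions, so they too could mistake the tablet for the PCP raising the subject. It would be wrong to infer that misattribution is impossible in SO.
- The tablet assesses readiness, which is not the same as enhancing motivation, and its patient-facing step as described negotiates no plan. The clear overlap is with feedback. The printed summary comes from the decision support handed to the PCP, so it is not clearly separate from the PCP's work.
- No patient-facing tablet feedback is described at follow-up, so exposure is mainly at baseline.
- The error rates are assumed. In every scenario of Step 2, a false significant result is less likely than not.

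A reader might also infer that the whole primary outcome is compromised. The documents do not support that. Chart review is a listed source in both conditions and is not patient-reported, and section 3.2.a does not say that the exit survey defines the event.

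The objections do not supply a safeguard or analysis directed at this risk; the plan states none.

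**Conclusion.** The concern holds as a risk to one source. Tablet feedback given only in SUSIT may inflate the exit-survey measure of the primary outcome relative to SO, mainly through baseline reports, and the plan neither guards against this nor measures it.

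The size is unknown. It depends on the base rate of PCP intervention and on the difference in false-positive rates between conditions, and the documents give neither. Under the assumptions in the working, with no true effect, the false odds ratio is 1.18 to 1.85 in Step 2 and 1.11 to 3.50 in Step 3.

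It would go too far to rest the study's conclusion on a corrected odds ratio. BAS-negative SUSIT visits may be few: if there were 22 (assumed) and the survey agreed on 19, the 95% Wilson interval for specificity would be 0.67 to 0.95, which cannot separate 0.80 from 0.90. The protocol gives no BAS threshold for receipt, visit-level error rates do not carry over directly to a patient-level outcome, and nothing shows that SUSIT error rates apply in SO. The correction belongs beside the main result as a sensitivity analysis.

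**What to change.** Add three analyses to section 3.2.a:

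1. **Survey against audio.** Pre-specify the BAS score or items that count as receipt. For SUSIT visits with both a recording and an exit survey, report agreement, sensitivity and specificity of the survey against coded receipt, with confidence intervals and with baseline visits shown separately. State how many visits lack a recording, since recording needs separate authorization and can be paused or stopped.
2. **Chart-review sensitivity analysis.** Repeat the SUSIT versus SO model with chart-review receipt as the outcome, among patients with a chart review, and report coverage by condition.
3. **Misclassification sensitivity analysis.** Beside the uncorrected odds ratio, report a corrected one at patient level. In each condition, corrected rate = (observed rate − (1 − specificity)) / (sensitivity + specificity − 1). Use patient-level SUSIT error rates informed by item 1, and stated ranges for both SO sensitivity and SO specificity.

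State in advance that the claim of more PCP-delivered intervention will be qualified if these analyses do not support it.

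Leave the exit-survey wording as it is. Section 5.2 already provides for SO participants who have finished all study visits, so rewording now would confound wording with condition.

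The cost is a little more analysis of data already planned for collection and coding. The intervals will be wide if few SUSIT visits are BAS-negative, and the result may be less favourable.

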## **2. Characteristics of the research population**

Main study sites: Bellevue Hospital Center (BHC) and Gouverneur Health will serve as the main study sites. Both sites serve a diverse and medically underserved population. The proposed study will recruit patients and primary care providers (PCPs) from the adult primary care clinics and the virology clinic at Bellevue Hospital Center. Up to 265 participants will be enrolled in the study. In Phase 1, up to 50 patients from Gouverneur Health and 35 PCPs from Bellevue and Gouverneur will participate in CDS development. In Phase 2, 150 patients and up to 30 PCPs from all study sites will participate.

Enrollment only sites: Two additional clinics are enrollment only sites, with limited study activities, in Phase 2 only. The enrollment only sites are two HIV clinics that function as primary care clinics. These sites are located at Lincoln Hospital in the Bronx, and Kings County Hospital in Brooklyn. Including these sites in the study offers an opportunity to understand the feasibility and impact of the SUSIT approach in a larger and more geographically diverse population of HIV primary care patients, but does not change the overall study aims or design. Enrollment only sites will have the same inclusion and exclusion criteria. The patients and PCPs from these sites are included in the overall limit (maximum 150 patients and 30 PCPs in Phase 2) for enrollment across all study sites.

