## **2.2. Inclusion and exclusion criteria**

Primary Care Providers: Up to 65 PCPs are anticipated to participate in the study. In Phase 1, up to 35 PCPs from Gouverneur Health and Bellevue will participate in content development, usability testing and clinical testing of the clinical decision support tool. In Phase 2, up to 30 PCPs from Bellevue Hospital will participate. Participating PCPs can be medical doctors (MDs), doctors of osteopathic medicine (DOs), nurse practitioners (NPs), or physician assistants (PAs). Medical students and residents are not included. There are no additional eligibility or exclusion criteria for providers.

**Patients:** Up to 200 patients are anticipated to participate (50 in Phase 1, and 150 in Phase 2). Patients are recruited if they have a medical visit with one of the participating PCPs. Because the SUSIT self-administered screening instrument is currently available in English and Spanish, the study is restricted to English and Spanish speaking patients.

Inclusion criteria:

- Substance use screening results (collected using the tablet-based screening tool) indicating current moderate risk drug use, based on a substance specific involvement score (SSIS) indicating current (past 3 months) use of at least one drug with a moderate risk level (SSIS 4-26), in the absence of any high-risk drug or alcohol use (SSIS 27+);
- 18 years or older;
- English and Spanish speaking;
- Presenting for visit with a participating PCP; and
- Able to provide informed consent
- Available to complete two follow up visits (3 months and 6 months after baseline appointment)

Exclusion criteria:

- Prior participation in the study (i.e. participation in the SO study phase would preclude participation in the SUSIT phase);
- Attending a formal addiction treatment program (not including informal treatment such as Alcoholics Anonymous, Narcotics Anonymous), in the past 3 months;
- Pregnant (based on self-report).
- Unable to read text on the tablet-based screening tool, or physically unable to operate the tablet.

The PI's prior study in this clinic indicates that 17% of all patients will meet eligibility criteria.

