For patients who enroll in Phase 2, the researchers will collect contact information (telephone numbers, address, and email address) to facilitate study retention and scheduling of follow-up study visits. Because in this urban safety net primary care population patients may have unstable housing, participants will also be asked to provide contact information for at least three close

contacts (family, friends) who the researchers could contact by phone or mail if they were unable to locate the participant using their personal information. No personal information will be shared with these close contacts. We will also ask if they work with a social worker or case manager, and if they would allow us to contact them if we were unable to locate participant using their personal information.

For participants in the SUSIT study phase, the research staff will send a clinical reminder to the patient's PCP at each scheduled medical visit that occurs during the study period. Research staff will send these reminders using email or the clinic's secure EHR-integrated message system. It will be sent directly to the PCP only, and will not be accessible to any other than the PCP and the research staff who sent the message. The message sent to the PCP will include the patient's name, medical record number, and substance use screening results from the baseline visit.

At enrollment only sites, the NYU research staff will not access the EHR to view patient information or to communicate with the patient's PCP. The research staff will communicate with PCPs through either secure H+H System email or secure NYU email communications only, and will work with participants and front desk staff to determine the patients' upcoming scheduled appointments.

Transcripts will not contain names or other information that could be used to identify individuals. Participants will be informed in the informed consent sheet that these sessions are recorded for purposes of transcription. Data will be analyzed and reported anonymously.

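### Two HIV clinics feed the SUSIT condition only and the primary model has no pre-specified site term, so part of any hospital difference can enter the SUSIT odds ratio

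*Combined protocol and SAP*

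**What the plan says.** Section 2 introduces two HIV clinics, at Lincoln and Kings County hospitals, as enrollment only sites. It says of them: "The patients and PCPs from these sites are included in the overall limit", meaning the Phase 2 maximum of 150 patients and 30 PCPs. Section 3.1.b adds that "Enrollment only sites will participate only in the Phase 2 SUSIT condition".

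Other text still describes Phase 2 without these clinics. Section 2.2 says "In Phase 2, up to 30 PCPs from Bellevue Hospital will participate", and Section 3.1.b opens with "Phase 2 is conducted at Bellevue Hospital", naming its adult primary care and virology clinics.

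The primary analysis (Section 3.2.a, quantitative analysis) is a multilevel logistic regression with treatment condition as the key explanatory variable, "with a random intercept and patients nested within primary care providers". Patient-level and PCP-level covariates "can be added to the multilevel logistic regression analysis if they are significantly related to the odds of intervention". The examples given are substances used and provider attitude score; site is not mentioned. The section defines no analysis set and excludes nobody.

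On measurement, Section 3.1.b says "Research staff will perform a structured chart review", and Table 1 lists chart review as one source for the primary outcome. Section 4.3.c says "At enrollment only sites, the NYU research staff will not access the EHR to view patient information".

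**The concern.** At the added clinics, site and condition coincide: every patient is a SUSIT patient. If PCPs there discuss substance use more or less often than Bellevue PCPs in ordinary practice, that difference shifts the SUSIT group and leaves the SO group untouched.

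The PCP random intercept does not fully protect against this. It assumes that PCP effects are unrelated to condition. PCPs at the added clinics see SUSIT patients only, so the assumption fails whenever the hospitals differ. The primary odds ratio would then partly compare hospitals.

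If chart review is not possible at these clinics, outcome ascertainment may also differ, again in SUSIT alone.

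**Working it through.** The plan has no figure to reproduce here. It gives no event rate, effect size, power or between-PCP variance; only 75 + 75 = 150 can be checked, and it agrees.

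**Inputs from the documents.** 75 patients per period (Section 1); ten PCPs (Section 1.3), taken here as the Bellevue PCPs; added sites in SUSIT only (Section 3.1.b); condition plus PCP random intercept (Section 3.2.a).

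**Assumed inputs.** True SUSIT odds ratio 1; usual-care rate 30% at Bellevue and 18%, 40% or 50% at the added clinics; k = 15, 25 or 40 of the 75 SUSIT patients from those clinics; 10 added PCPs; the same ten Bellevue PCPs in both periods; PCP SD 0.5 or 0.8 on the logit scale; no time trend.

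**Step 1, arithmetic without clustering.** The SUSIT rate is p = [(75 − k) × 0.30 + k × 0.50] / 75, and the apparent odds ratio is p/(1 − p) divided by 0.30/0.70 = 0.429.
- k = 15: p = (18 + 7.5)/75 = 0.340; odds 0.515; OR 1.20.
- k = 25: p = (15 + 12.5)/75 = 0.367; odds 0.579; OR 1.35.
- k = 40: p = (10.5 + 20)/75 = 0.407; odds 0.685; OR 1.60.

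**Step 2, the plan's model.** logit P(Y = 1) = β0 + β1·SUSIT + u(PCP), with u normal. Fitted by maximum likelihood (15-point Gauss-Hermite quadrature), likelihood-ratio test at 5%, 2000 replicates per scenario. Cells show the median OR and the false-positive rate.

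| Added-clinic rate, PCP SD | k = 15 | k = 25 | k = 40 |
|---|---|---|---|
| 50%, SD 0.5 | 1.18, 7% | 1.31, 11% | 1.49, 18% |
| 50%, SD 0.8 | 1.18, 8% | 1.27, 11% | 1.42, 15% |
| 40%, SD 0.5 | 1.09, 6% | 1.14, 7% | 1.23, 9% |
| 18%, SD 0.5 | 0.91, 6% | 0.85, 7% | 0.76, 10% |

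Against Step 1, the random intercept absorbs some of the hospital difference, but most of it remains.

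**Step 3, alternatives.** With a fixed term for added site, or with Bellevue patients only, the median OR is 1.00 to 1.03 and false positives are about 5%. If the plan's covariate rule were applied to site (added only when significant; 50% vs 30%, SD 0.5), the median OR is 1.10, 1.13 and 1.16 for the three values of k, with 5–6% false positives.

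**Step 4, precision.** SD of the log OR without and with the site term (50% vs 30%):
- k = 15, PCP SD 0.5: 0.365 and 0.391 (ratio 1.07).
- k = 25, PCP SD 0.5: 0.372 and 0.416 (1.12).
- k = 40, PCP SD 0.5: 0.381 and 0.492 (1.29).
- k = 40, PCP SD 0.8: 0.424 and 0.492 (1.16).

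**Step 5, different assumptions.** A separate simulation used 4 added PCPs and 400 replicates. It gave a median OR of 1.21 with 8.7% rejection (site odds ratio 2, k = 25) and 1.47 with 18.2% (site odds ratio 3, k = 40). At PCP SD 1.0 (site odds ratio 2, k = 25) the OR was 1.12. With the site term, all scenarios gave 0.97 to 1.00 and 3.0–5.2% rejection.

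**The case against.** Several points on the other side are sound.

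- **Inclusion is inferred.** No section defines the analysis set, two sections place Phase 2 at Bellevue, and Section 2 says the added sites leave aims and design unchanged. What is certain is that the set is undefined and the sections conflict.
- **The size is assumed.** Share, hospital gap, event rate and PCP variance are all absent from the documents. Fewer added PCPs would reduce the bias: at 50% vs 30%, SD 0.5 and k = 40, the median OR is 1.45 with 4 added PCPs and 1.37 with 2, against 1.49 with 10.
- **The covariate rule is open-ended.** A PCP's site is a PCP-level attribute, so site could be added. Step 3 shows that this mitigates the bias but does not remove it, and the rule is discretionary.
- **The site term has a price.** It leaves 60, 50 or 35 SUSIT patients informing the condition effect. At 40% vs 30% (SD 0.5, 10 added PCPs), root mean squared error of the log OR is slightly worse with the term: 0.408 vs 0.395, 0.439 vs 0.414 and 0.501 vs 0.459. At 50% vs 30% the term does better.
- **A yes/no term is coarse.** It does not adjust for a changing mix of Bellevue's primary care and virology clinics between periods.
- **Chart review is secondary here.** The exit survey is collected in both conditions, and Section 5.2 already makes chart review depend on consent.

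These limit how firmly the size can be stated. None of them removes the bias if the patients are analysed as the plan now reads.

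**Conclusion.** The concern holds. If the added-site patients enter the primary model as written, part of any hospital difference in usual practice loads on the SUSIT odds ratio, in either direction. Over the ranges in Step 2, the median odds ratio under no effect runs from 0.76 to 1.49, and false positives from 6% to 18%. These figures are illustrative. The bias is material only when both the share of patients from the added clinics and the hospital gap are large. It should be fixed, because it concerns the primary outcome and the remedy uses data the study will already have. The remedy does not touch calendar-period confounding, which is a separate limit of the pre-post design.

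**What to change.** In Section 3.2.a:
1. Define the analysis set for the primary outcome and say whether enrollment only patients belong to it.
2. Pre-specify a fixed term for enrollment only site (yes/no), kept whatever its significance, so that the condition effect is estimated within Bellevue.
3. Add a sensitivity analysis limited to Bellevue PCPs with patients in both periods.
4. Report the enrollment only sites separately, as SUSIT-only data.
5. State which outcome sources apply at those sites.

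Reconcile Section 2.2 and the opening of Section 3.1.b with Section 2 and the enrollment only paragraph of 3.1.b. Reconcile the chart-review text and Table 1 with Section 4.3.c. State calendar-period confounding as a remaining limitation.

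The change is to wording only and needs no new data. Its statistical cost is the loss of precision in Step 4: 7% to 29% on the SD of the log odds ratio at PCP SD 0.5. The effect of the tool at the added clinics cannot be estimated in any case, because they have no SO patients.
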